8 PROTOCOL

8.1 Subject Enrolment

No study-specific procedure, eCRF or form associated with this study can be completed using a patient's personal and/or medical information until written Informed Consent is obtained for that Subject (see Section 5.3. Definition of Subject Enrolment).

8.1.1 Subject Screening

All patients who present with osteoarthritis, post-traumatic arthritis, or a failed previous implant affecting the knee, and are candidates for cementless TKA, and who generally meet the study requirements, will be screened for eligibility and will be listed on the Screening and Enrolment Log in order to document that the Subject selection was unbiased. The date of screening, the results of screening (included or not) and if applicable, the primary reason for not including the patient (e.g., does not satisfy eligibility criteria, not interested in participating) will be recorded on this log. The original log is to be retained at the Site and a copy sent to the Sponsor regularly during enrolment.

Eligible patients who agree to participate in the study will be required to sign an Informed Consent Document prior to any study-specific procedures being done. After signing the Informed Consent, study Subjects are defined as "enrolled" and site will complete the non-standard of care pre-operative data collection.

It is expected that complete data collection will be obtained for all enrolled Subjects, with the only exceptions being a Subject who is subsequently withdrawn (see section 8.4 Discontinuation of Subject Participation for details).

8.1.2 Subject Informed Consent

The Principal Investigator is responsible for ensuring that no Subject is included in the study without adequate informed consent being provided. Failure to obtain and properly document this process is in violation of ISO 14155, the Declaration of Helsinki, and this study protocol.

All Informed Consent Documents (ICD) must have favorable opinion of the responsible IRB/EC and reviewing Regulatory Authority, as applicable (Section 12.1). Consent of a Subject needs to be from the Subject themselves and documented on an ICD in the primary language of the Subject as well as the process of consent documented in the Subject's source medical records. Each Subject will be allowed sufficient time to decide whether they wish to participate in this clinical investigation. Written informed consent from the Subject MUST be obtained before any of the study-specific procedures are performed and PRIOR TO the Day of Surgery. Acquiring consent on the day of surgery will be considered a Protocol Deviation. Note: On review and approval by Sponsor, a CRF completed as part of an investigator's standard of care (e.g. KOOS) can be used as a source document for study required PROMs after the study informed consent has been signed.

Screening, consenting and enrolment are illustrated in Figure 8-1. The Investigator or trained designee preliminarily screens to determine if a patient generally meets the eligibility criteria for the study. If so, the Investigator or trained designee shall offer study participation to those patients. Having explained the study intent to the Patient, the Investigator or trained designee shall offer to answer any of the Patient's questions. If the Patient then agrees to participate, his or her willingness must be documented via a signature and date on the IRB/EC's approved ICD and this document subsequently countersigned and dated by the person taking consent with a copy of the signed consent document being provided to the study Subject. This full consent process must be documented by the Investigator or trained designee.

Upon successful completion of the consent process, the Patient is enrolled and is identified as a Study Subject.

[figure not shown]

Figure 8-1: Screening and Enrolment Process

8.1.3 Subject Identification Numbering

The database assigns Subject ID numbers after consent is obtained and data are entered into the Electronic Data Capture system.

Each site is identified uniquely, e.g., PPD - followed by PP for the first Subject at the site, PP for the second Subject and so on. Together the Site number and the Subject number will then become the unique identifier of the Subject and will be recorded on each page of the eCRF and on the Subject Screening & Enrolment Log. For example, the first three enrolled patients at site #PPD would be: PPD

In the instance of a Subject being enrolled, a number assigned and subsequently the Subject is deemed ineligible prior to receiving the ATTUNE Cementless FB knee, a Subject Completion/Discontinuation eCRF should be completed and the Subject will be recorded as a screen failure on the Screening & Enrolment log. In the case of pre-operative withdrawals, a further Subject will be enrolled to replace the withdrawn Subject in order to ensure a minimum of 600 Subjects are implanted: a minimum of 300 CR FB (CR or MS Tibial Insert) and 300 PS FB (PS Tibial Insert) configurations with up to 300 cementless patellae combined across both configurations (if market available). Once a Subject identification number is assigned, it may not be reused. Refer to Section 8.4.1 Enrolment Replacement Rules.

8.2 Study Procedures

This section is applicable to enrolled study Subjects. The study Surgeons have selected to implant a total knee arthroplasty using cementless fixation as their standard of care. Therefore, this study does not limit the procedures involved in the treatment of the subject. The pre-operative, anesthesia, general operative procedures post-op care, and follow up are not research procedures, and therefore are not restricted by the study and are regardless of the research.

This section details the study requirements in terms of the pre-operative, operative, and post-operative management of Subjects. Visit evaluations include clinical and radiographic evaluations and Subject self-assessments. eCRFs must be submitted to DePuy Synthes Products Inc. as outlined in Section 11.7 Case Report Form Completion and Data Submission.

The patient reported outcome instruments AKS, KOOS, FJS-12, and EQ-5D-5L are compulsory at all sites. PROMs are compulsory for those Subjects whose primary language is one in which the tools are available. Sites will be advised during training whether validated translations are available in the local language(s) applicable to the Site.

8.2.1 Detailed Instructions on Data Collection

The following evaluation tools are to be used to collect and evaluate study subject outcomes preoperatively, intra-operatively and post-operatively as outlined in Table 8-1. Patient reported outcomes (in italics) will be provided in hard copy printed sets for completion by the study subject during a clinic type visit.

The PROM assessments should be the first assessments administered on the visit day. Pre-operative PROMs should be performed within the preferred visit window (-90d to -1d prior to surgery). **Note: The required window allows the preoperative assessment to be completed 180 days to 1 day prior to surgery.** Each of the questionnaires are to be completed ONLY by the Subject, and usually takes 2-3 DSJ_2019_05, Rev D (FINAL)

DePuy Synthes Products, Inc. - Confidential

24 August 2022

minutes per questionnaire to complete. The research team member will provide an official copy of the PROMs to the Subject. The Subject is then to read and complete the form themselves. The research team member is not permitted to read out any of the questions or mark Subject answers on the form. Subjects that are not able to read and complete the questionnaires themselves should not be included in the study (as per Inclusion Criteria F). Subjects should be encouraged to answer all questions.

It is best practice to administer PROMs in reverse recall order (longest to shortest recall duration) and general outcomes to specific outcomes, e.g., in order of subject completion by Subject: AKS, FJS-12, KOOS, and EQ-5D-5L.

Sponsor Approved PROMs by Mail Method (postoperative follow-up only): The packets should be set up with the order of PROM completion as would be done in clinic and should include only those PROMs translated in the Subjects' language (i.e. the Subject portion only of the AKS, KOOS, FSJ-12, & EQ-5D-5L). The packets will be mailed to the Subject along with a cover letter approved by reviewing IRB/ECs. At a minimum, the cover letter should include instructions on how to complete the PROMs and how to mail them back to the site. NOTE: The surgeon portion of the AKS and radiographs are not required with this option and will not result in a protocol deviation if Sponsor approved.

Table 8-1: Data collection, with Subject Completed forms in italics

Case Report Form	Details of Evaluation	Pre-Op/ Intra- op/Post—Op
Subject	System generated Subject ID Number	Pre-Op Only
Inclusion/Exclusion	Verification of Subject as per Inclusion / Exclusion Criteria	Pre-Op Only
Demographics	Record of relevant Subject demographic information	Pre-Op Only
Medical and Surgical History	Authorized medical personnel will collect Subject's relevant medical and surgical history relating to any previous cardiovascular, neurologic, general medical history and previous surgeries on the affected knee.	Pre-Op Only
Study Visit	Assists study site to verify that study visit occurred in the appropriate interval and by the appropriate means (at clinic, by mail or by phone). Prior approval from Sponsor required for Site to exercise mail or phone options.	Pre-op & Post-op
Pre-operative AKS 2011 ³⁹ Patient reported section	Pre-op O	
Post-operative AKS 2011 – Patient reported section	below. The total time for completion per study Subject is approximately 20-25 minutes.	Post-op Only

Case Report Form	Details of Evaluation	Pre-Op/ Intra- op/Post—Op
Knee injury and Osteoarthritis Outcomes Score (KOOS)		Pre-op & Post-op
Forgotten Joint Score (FJS-12)		Post-op
EQ-5D-5L		Pre-op & Post-op
AKS 2011 – Surgeon reported section	The Investigator or appropriately trained designee must complete the OBJECTIVE KNEE INDICATORS section that assesses the Subject's alignment, instability, and joint motion.	Pre-op & Post-op
Image/Scan	Date and details of Radiographs collected at each required timepoint. AP/PA, Lateral and Skyline (as applicable) radiographs will be obtained post-operatively (Section 8.2.7) Pre-operative radiographs (taken as per the Sites standard of care) can be taken up to -180 days prior to the surgical event (or older at the discretion of the PI). Pre-operative Radiographs provide background information only, and do not constitute either a primary or secondary endpoint. Post-operative radiographs must be taken as per study-required Image Acquisition Protocol (IAP).	Pre-Op & Post-Op
Radiographic Evaluation	Surgeon evaluation of post-op radiographs	Post-Op
Study Procedure	Description of Subject's surgical procedure including such items as configuration used, surgery time, tourniquet time, surgical technique details etc.	Intra-Op
Device Log	Identification of devices implanted, including product codes, lot numbers and Universal ID code/device identifier (if available).	Intra-Op
Adverse Event Summary	Summary of all recorded AEs for each subject	As required (Intra- Op and/or Post- Op)
Adverse Event	Includes diagnosis, date of onset, treatment and classification of the AE.	As required (Intra- Op and/or Post- Op)

Case Report Form	Details of Evaluation	Pre-Op/ Intra- op/Post—Op
Device Deficiency Summary	Notes whether there were any device deficiencies	As required (Intra- op or Post-Op)
Device Deficiency	Nature of device deficiency and implications of that deficiency (both implant and instrument related)	As required (Intra- op or Post-Op)
Protocol Deviation Summary	Summary of all recorded Protocol Deviations for each subject	As required (Preop, Intra-Op and/or Post-Op)
Protocol Deviation	Nature of deviation that has occurred and reason why	As required (Pre- op - Post-Op)
Subject Completion / Discontinuation	Reason for follow-up being concluded (e.g., completed study requirements, consent withdrawn)	As required (Pre- op - Post-Op)

8.2.2 Pre-operative Management

Prior to surgery, the data in Table 1-1 (the Time & Events Table) must be collected for each enrolled Subject. The interval for obtaining the Informed Consent and pre-op assessments is from -90 days through day -1 (1 day prior to surgery) as designated on the Time & Events Table (Table 1-1). The -90 day time frame is important to support PROMs being collected closer to the time of surgery since it is anticipated that there may be deterioration in function as the patient awaits surgery.

The interval for obtaining preoperative radiographs is extended to -180 days (or older at discretion of PI*) to day -1 (day prior to surgery) so that study Subjects would not need to have repeat radiographs if any radiographs that had been taken as standard of care prior to the Subject being enrolled were the required views. This will be allowed to minimize the study Subject's unnecessary exposure to radiation.

*Note: it would be preferred if the radiographs were taken from -90 days through -1 day, however, if radiographs are available that exceed the 180 day maximum timepoint, they can still be used if they are thought to be acceptable for preoperative surgical planning (per the surgeon's standard of care) at the discretion of the Principal Investigator (PI). If the preoperative x-rays are not able to be uploaded to the MMI system, submitted to MMI via CD, available via hard copy for courier to MMI, or are not deidentifiable, they should be repeated.

Once written informed consent is given, the below will be followed:

- Pre-operative Patient Reported Outcome questionnaires, Inclusion/Exclusion, Demographics, Medical and Surgical History, 2011 American Knee Society Score surgeon (AKS) and Image/Scan CRFs are to be completed.
- The TKA surgical details and all intra-operative complications, regardless of their relationship to the procedure or device, are captured on eCRFs for subsequent analysis.
- In clinic follow-up intervals include 6 weeks, 6 months, 1 year, 2 years and 5 years postoperative. Post-operative radiographs will be taken at either the 6-week OR the 6-month follow-up (if x-rays are taken as standard of care at both visits then the 6-week x-rays should be used) and again at 1 year, 2 years and 5 years.
- Subjects will be contacted by phone or by mail at 3 and 4 years post-op to optimize
 accuracy of the survivorship data, enable timely capture of AEs and maximize the chance
 of good long term follow-up.

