4 STUDY RISK / BENEFIT ANALYSIS

4.1 Potential Risks to the Subject

Any surgical procedure poses a potential risk and the procedures undertaken as part of this clinical investigation are no exception. There are known risks associated with the method of anesthesia (general, epidural, local). In addition, there are risks associated with implantation of a device. The risks associated with the study devices are similar to those of any primary, cementless total knee replacement. A full description of the potential risks related to the ATTUNE Cementless FB is included in the Instructions for Use. In addition to the risks provided in the product IFU, bleeding or excessive blood loss, transfusion reaction, or death may occur. These risks may occur with any total knee arthroplasty procedure.

Since it is anticipated that study subjects would be undergoing total knee replacement with a Cementless total knee system whether or not they enroll in the study, there are no foreseeable study-related risks involved with study participation except for the possibility of additional radiation exposure and / or unintentional disclosure of protected health information. Participation in this study may require study subjects to have between 1 and 3 additional X-ray examination(s) that they otherwise would not receive if they did not take part.

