8.2.5 Radiographic Procedures

Radiographs are to be obtained pre-operatively and at either the 6 week or 6 month visit (1st follow-up/baseline evaluation, timeline as per the Site's standard of care) and again 1, 2 and 5 years post-operatively (within the respective windows specified in this protocol). Pre-operative radiographs are to be collected as per the Site's standard of care. AP/PA and Lateral views are required for all Subjects at the above post-operative timepoints. Skyline views should also be collected post-operatively for Subjects with an implanted patellar component. Investigators will complete questions within the eCRF regarding interpretation of the radiographs for each required set of radiographs.

Radiographic guidelines regarding image collection will be provided to Sites. Sites are also required to send all radiographs collected during the course of the study to an external image analysis facility; training on the process to transfer images will be provided prior to study start.

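### Section 8.2.2 asks for pre-operative X-rays to be repeated when they cannot be transferred or de-identified, although no planned analysis uses them and extra radiation is a named study risk

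*Combined protocol and SAP*

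**What the plan says.** Five places bear on this point.

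- **Section 8.2.2, the window.** Pre-operative radiographs may date from 180 days before surgery, or earlier at the investigator's discretion, so that usable standard-of-care films need not be taken again. The reason given is: "This will be allowed to minimize the study Subject's unnecessary exposure to radiation".
- **Section 8.2.2, the note that follows.** "If the preoperative x-rays are not able to be uploaded to the MMI system, submitted to MMI via CD", or are not "available via hard copy for courier to MMI, or are not deidentifiable, they should be repeated".
- **Table 8-1 (section 8.2.1).** "Pre-operative Radiographs provide background information only, and do not constitute either a primary or secondary endpoint".
- **Section 4.1.** The section sees no foreseeable study-related risk "except for the possibility of additional radiation exposure and / or unintentional disclosure of protected health information". It then puts a number on the radiation: "Participation in this study may require study subjects to have between 1 and 3 additional X-ray examination(s") beyond those they would otherwise receive.
- **Section 8.2.5 and the Table 1-1 legend.** "Pre-operative radiographs are to be collected as per the Site's standard of care". The first post-operative film is taken at 6 weeks or 6 months, "timeline as per the Site's standard of care) and again 1, 2 and 5 years post-operatively". Section 8.2.5 also has sites send all study radiographs to the external imaging facility, and Table 1-1 marks the pre-operative image as one to be taken and submitted.

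**The concern.** Section 8.2.2 sets out to avoid repeat films and then calls for them on grounds unrelated to whether the film is any good. A film may be entirely usable at the site and still fall under the rule because it cannot be moved or stripped of identifiers.

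A subject would then be exposed again for a failure in data handling, and no study result would change. This sits badly with section 8.2, which says that pre-operative procedures are not research procedures, and with section 4.1, where additional radiation is one of only two risks attributed to participation. An ethics committee reading section 4.1 cannot tell whether this exposure is within the stated number.

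**Working it through.** **Step 1: what triggers the repeat.** Section 8.2.2 gives two triggers. Either upload, CD and hard-copy courier are all unavailable, or the film cannot be de-identified. The first concerns transfer and the second privacy. Neither depends on image quality, view or age.

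**Step 2: what the repeated film would be used for.**

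| Possible use | What the plan provides |
|---|---|
| Primary or secondary endpoint | Excluded by Table 8-1 |
| Investigator's radiographic evaluation | Post-operative only in Table 8-1; no pre-operative entry in that row of Table 1-1 |
| Radiographic secondary endpoint (sections 6.2 and 9.8.4.2) | Post-operative time points only |
| Storage at the imaging lab | Yes (Table 1-1 legend, section 8.2.5) |

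Only storage is left.

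**Step 3: comparison with the films that are analysed.** Post-operative films support a secondary endpoint. They are nevertheless optional when a visit is done by mail and telephone (Table 1-1 legend, section 8.2.4.1), and with sponsor approval their absence is not a deviation (section 8.2.1). The plan thus tolerates a missing endpoint film but asks for a new exposure to replace an untransferable background film.

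**Step 4: can the 1 to 3 in section 4.1 be reproduced?** The plan gives no derivation and no count of standard-of-care films. Treat one visit's set of views as one examination (an assumption). Let *s* be the number of scheduled post-operative sets that standard care already provides, and *r* = 1 if the pre-operative film is repeated, otherwise 0. The schedule has 1 (6 weeks or 6 months) + 1 (year 1) + 1 (year 2) + 1 (year 5) = 4 post-operative sets, so

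additional examinations = (4 − *s*) + *r*.

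| *s* (assumed) | Without repeat (*r* = 0) | With repeat (*r* = 1) |
|---|---|---|
| 0 | 4 | 5 |
| 1 | 3 | 4 |
| 2 | 2 | 3 |
| 3 | 1 | 2 |
| 4 | 0 | 1 |

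The stated range arises in more than one way. With no repeat, *s* = 1 to 3 gives 3 to 1. With a repeat, *s* = 2 to 4 also gives 3 to 1. If 1 to 3 covers post-operative films only, a repeat makes it 2 to 4. If it already allows for a repeat, it stays 1 to 3. The documents do not settle which applies.

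**The case against.** The strongest defence is that the rule has an operational reason. Section 8.2.2 says that the Table 1-1 data must be collected for each subject, Table 1-1 marks the pre-operative image for submission, and section 8.2.5 wants all study radiographs at the external facility. Standard of care governs how the film is taken; the repeat serves the separate submission requirement. For transfer, the rule applies only after three routes have failed, so it may seldom be used. This explains the rule and shows that any fix must also reach the submission requirements. It does not supply a use for the image.

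A reader might infer more than the text supports in four ways.

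- **That participation will exceed three additional examinations.** Section 4.1 counts films a subject would not otherwise have, and gives an expected range rather than a cap. The 4 or 5 sets in the schedule include films that may be routine. If the first post-operative film is routine, years 1, 2 and 5 give exactly 3. An excess is possible but not shown.
- **That the repeat is strictly mandatory.** The wording is *should*. Sites may still treat it as binding, because departures from the protocol are recorded as deviations (section 8.2.6).
- **That every affected film had already been accepted for surgical planning.** In section 8.2.2 that condition applies only to films older than 180 days, while the repeat sentence covers all pre-operative films. The point needs only that the triggers ignore adequacy.
- **That section 8.2.5 flatly forbids the repeat.** The tension is mild, since that section also contains the submission requirement. The clear inconsistency is within section 8.2.2.

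**Conclusion.** The point holds as an inconsistency within section 8.2.2, and between it, Table 8-1 and section 4.1. The plan calls for an exposure on transfer or privacy grounds alone, for an image that no planned analysis uses, after stating that it wants to avoid repeat films.

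The size is at most one additional examination per affected subject. The number affected is unknown, because the documents give no rate of transfer or de-identification failure. Whether the total passes 3 depends on each site's standard of care, which is not given either. What subjects are told could not be checked, because the consent pages are not in the reviewed text.

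There is no effect on sample size, power, any endpoint or the primary analysis. The case for changing it rests on subject safety and an accurate risk statement.

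**What to change.** Reconcile section 8.2.2 with section 4.1, Table 8-1, the Table 1-1 legend and section 8.2.5:

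1. In section 8.2.2, remove the repeat as a study requirement where the only problem is transfer or de-identification.
2. Record such a film on the Image/Scan eCRF as available at site but not transferable, with no protocol deviation.
3. Add a matching exception to the submission requirement in the Table 1-1 legend and in section 8.2.5. Otherwise those passages would still demand the image.
4. Leave any imaging needed for care to the site's standard of care.

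If the sponsor prefers to keep the repeat, section 4.1 should say whether the 1 to 3 additional examinations include it. That figure should not be replaced by the scheduled count of 4 or 5, which measures something different.

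The cost is a few sentences in an amendment and probably a few background images missing at the imaging lab. No endpoint loses data.
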